#### 6.5.3 Concomitant Procedures

Any diagnostic, therapeutic, or surgical procedures performed during the trial will be recorded in the eCRF, including the date and reason for the procedure.

# 6.5.4 Surgical Resection Following Initial Response

Investigators may choose to resect solitary lesions in patients on study after consultation with the Medical Monitor. Any such resections should follow confirmation of tumour shrinkage by CT or MRI scan and, preferably, after a subsequent scan indicates no further shrinkage. Patients with a PR who go on to have surgical resection of remaining disease will be considered a PR.

#### 6.6 PREGNANCY

All patients who are not either surgically sterilised, postmenopausal (a woman who is ≥45 years of age and has not had menses for greater than 18 months without an alternative medical cause will be considered postmenopausal), or not heterosexually active for the duration of the study must be instructed to use adequate, effective contraception whilst taking part in the study and for at least 6 months after discontinuation of treatment.

Acceptable adequate, effective methods of contraception include intrauterine device (IUD), intrauterine hormone releasing system (IUS), oral contraceptive (progestogen-only oral contraception that does not inhibit ovulation is not an acceptable method), bilateral tubal occlusion, vasectomised partner, and subdermal implant. True abstinence is allowable for prevention of pregnancy but any women of child-bearing potential who choose this method must continue to have pregnancy tests.

In the event of a pregnancy, whenever possible, consent should be obtained for it to be followed to term, any premature terminations reported to Bionical-Emas, and the status of the mother and child should be reported to the Sponsor after delivery and at important developmental milestones during the first year.

Page 41 of 98

# **6.6.1** Female Patient's Pregnancy

Patients who become pregnant during the study must be withdrawn from the study immediately.

Patients must be instructed to notify the Investigator if it is determined after completion of (or withdrawal from) the study that they became pregnant during the study within 6 months of last dose on study.

# **6.6.2** Male Patient's Partner's Pregnancy

Male patients must be instructed to notify the Investigator if it is determined that, during the study or after completion of the study, their partner became pregnant during the study.

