- 13. Patient is pregnant or breast-feeding. Female patients with reproductive potential must have a negative serum pregnancy test (β-human chorionic gonadotropin [β-hCG]) within 72 hours prior to first administration of study drug. Both women and men must agree to use a medically acceptable, effective method of contraception throughout the treatment period and for at least 6 months after discontinuation of treatment.
- 14. Patient has used depot corticosteroids in the 6 weeks before initiation of Screening (signing of the informed consent form [ICF]).

Page 38 of 98

- 15. Patient has a condition requiring systemic treatment with either corticosteroids (>10mg daily prednisone equivalent) or immunosuppressant drugs (e.g., azathioprine, tacrolimus, cyclosporin) within the 14-day period before the first administration of IMM-101. Inhaled or topical steroids, and adrenal replacement steroid doses >10mg daily prednisone equivalent, are permitted in the absence of active autoimmune disease.
- 16. Patient has received a blood transfusion within 4 weeks prior to initiation of Screening.
- 17. In the opinion of the Investigator, the patient is unable or unwilling to comply with the protocol.

For cohort A, patients meeting any of the following criteria are also ineligible to participate in this study:

1. Patient has received prior therapy with an anti-programmed cell death-1 (anti-PD-1), anti-PD ligand-1 (PD-L1), anti-PD-L2, anti-CD137 antibody, or anti-cytotoxic T-lymphocyte-associated antigen-4 (CTLA-4) agent.

For cohort B, patients meeting any of the following criteria are also ineligible to participate in this study:

1. Patient has previously experienced an AE related to anti-PD-1 therapy which, in the investigator's opinion, makes them unsuitable for further treatment with nivolumab.

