# 8.4.8 Pregnancy Test

A serum pregnancy test ( $\beta$ -hCG) will be conducted for all eligible females of child-bearing potential during Screening and at any other time during the study if pregnancy is suspected (Study Schedule of Assessments, in Appendix 1). Female patients with reproductive potential must have a negative serum pregnancy test ( $\beta$ -hCG) documented within 72 hours prior to the first dose of study drug.

The maximum volume of blood collected per patient at a single visit specifically for the safety endpoints will not exceed 10 mL Blood samples for immunomarker analyses are provided in Section 9.6

<sup>2 Only to be repeated if more than 7 days between screening test and commencing any study treatment (Visit 1)

<sup>3 Blood samples may be taken one day before the day of dosing (visit day).

Page 57 of 98

See section 6.6 for contraception requirements on study and handling of pregnancy.

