# 9.7.1 Pregnancy Reporting

Pregnancy is not considered an SAE. If a female participant, or the female partner of a male participant, becomes pregnant after exposure to study product, the pregnancy must be reported to Bionical-Emas within 24 hours of the Site Staff becoming aware of the Pregnancy. A Pregnancy Reporting Form must be completed and emailed or faxed to Bionical-Emas.

In the event of a pregnancy being reported after exposure to study product, the pregnant woman should be followed to completion/termination of the pregnancy and the outcome of the mother and infant should be reported in follow-up using the Pregnancy Reporting Form.

If a congenital anomaly or birth defect occurs, this must be reported to Bionical-Emas by the submission of a completed SAE form.

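### Section 6.6.2 asks men to notify only partner pregnancies that begin during the study, although their contraception period runs at least 6 months past treatment, so later exposed pregnancies may be missed

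*Protocol*

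**What the plan says.** **Notification.**

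- Section 6.6.2 has male patients tell the investigator if it is found, "during the study or after completion of the study, their partner became pregnant during the study".
- Section 6.6.1, the counterpart for female patients, refers to finding out after completion or withdrawal that "they became pregnant during the study within 6 months of last dose on study".
- Section 6.6 requires contraception "whilst taking part in the study and for at least 6 months after discontinuation of treatment". Exclusion criterion 13 (Section 6.2) applies it to both sexes: "Both women and men must agree to use a medically acceptable, effective method of contraception throughout the treatment period", followed by the same 6 months.
- Section 9.7.1 says that if a female participant, "or the female partner of a male participant, becomes pregnant after exposure to study product, the pregnancy must be reported" within 24 hours of site staff becoming aware. It gives no end date.

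**Testing.**

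- Section 6.6 allows true abstinence, but "any women of child-bearing potential who choose this method must continue to have pregnancy tests".
- Section 8.4.8 provides a serum test "during Screening and at any other time during the study if pregnancy is suspected".
- Section 8.4 provides one at screening and later if clinically indicated. Appendix 1 ticks it at Screening only, and footnote 6 adds a repeat if there is concern.
- Table 1 lists a test in the Treatment Phase on an as-needed basis, tied to no visit.

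The SAP (Section 5.15.4) only lists pregnancy test details.

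**The concern.** The contraception rule shows that the protocol treats the 6 months after treatment as a period in which conception should be avoided, for men as well as women. Section 9.7.1 treats a partner pregnancy after exposure as something the sponsor must hear about. The instruction meant to bring that information to the site stops earlier than both. A man whose partner conceives two months after his last dose is inside the precaution period and inside 9.7.1, but he has not been asked to tell anyone.

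What is at stake is safety information on partner and infant. Section 6.6 plans follow-up of the pregnancy to term and of mother and child through the first year, and that can start only if the site is told.

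The testing passages raise a separate and weaker question. One section states a standing duty for women relying on abstinence, while the operational sections mostly describe a repeat test that needs a trigger.

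**Working it through.** There is no sample size, power or error-rate figure to reproduce. The check is a comparison of passages plus one subtraction.

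**1. What 6.6.2 covers.** The sentence has two time phrases. The first (during or after the study) says when the pregnancy is discovered. The second (during the study) says when it began. Late discovery is therefore covered, but late conception is not.

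**2. Does another channel pick up a late conception?**

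- Section 9.7.1: the duty has no end date, but its 24-hour clock starts at site awareness. It does not create awareness.
- Sections 8.4.3 and 9.5: adverse event follow-up ends no later than 30 days after the last study treatment. Related SAEs are recorded beyond that, but 9.7.1 says pregnancy is not an SAE. A birth defect would be reportable, again only if the site learned of it.
- Sections 6.4 and 8.3: follow-up after the study collects survival and subsequent therapy, not pregnancy.

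None of these routinely asks about partner pregnancy after the study.

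**3. Length of the gap.** Inputs:

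- precaution period of 6 months (Sections 6.2 and 6.6);
- End of Study visit 28±7 days after the final IMM-101 dose, labelled Week 80 (Section 8.3);
- last nivolumab dose at Week 76 or 78 for completers (Section 7.6.1);
- month length of 30.4375 days (SAP Section 5.12).

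Assumption: a patient's time on study ends at his End of Study visit.

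- Precaution period: 6 × 30.4375 = 182.6, about 183 days.
- Interval from final IMM-101 dose to visit: 28 − 7 = 21 to 28 + 7 = 35 days.
- Uncovered, if IMM-101 is the last treatment: 183 − 35 = 148 to 183 − 21 = 162 days.
- Uncovered, if nivolumab is last given at Week 78 and the visit is at Week 80: 183 − 14 = 169 days.

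As a share of the precaution period: 148/183 = 81%, 162/183 = 89%, 169/183 = 92%.

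**4. The female instruction.** Section 6.6.1 mentions 6 months from the last dose but joins it to conception during the study with no connecting word. It can be read as both conditions together or as either one. Its clock starts at the last dose on study, whereas Section 6.6 counts from discontinuation of treatment.

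**5. Testing of abstinent women.** Appendix 1 has 40 numbered treatment visits (Weeks 0 to 78 every 2 weeks: 78/2 + 1 = 40). A routine pregnancy test is fixed to none of them, nor to the End of Study visit, and the visit lists in Section 8.2 omit it. Sections 8.4 and 8.4.8 and footnote 6 make a repeat test conditional. Table 1 carries no such condition but gives no frequency. Section 6.6 states the duty without a frequency either.

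**The case against.** The strongest reply is that 9.7.1 already makes every partner pregnancy after exposure reportable and that men are told to use contraception for 6 months. They may therefore report without further prompting. The patient information is also not available for this review and may say more than 6.6.2. This stands against any claim that such pregnancies will be missed. It does not remove the mismatch: 9.7.1 waits on awareness, and 6.6.2 is the protocol's own statement of what men must be told.

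A reader might infer that the whole 6 months is uncovered, or a quarter of a 24-month period (18 months of treatment plus 6). The documents do not support that. It would require the study to end for the patient at his last dose, but the End of Study visit comes later, and it would require every man to complete 18 months. Other readings shorten the gap further. Patients who stop for reasons other than progression, and for whom no further treatment is deemed appropriate or desired, stay on study for scans until progression (Section 6.4). The study as a whole ends at the last patient's last visit (Section 18.7.1).

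On testing, a reader might infer that a site following the schedule breaches 6.6, or that abstinent women go untested for up to 78 weeks. Neither follows. Table 1's as-needed entry can carry the 6.6 duty, Section 8.4.8 refers back to 6.6, and an unstated frequency is not a frequency of zero. What remains is wording that disagrees between sections.

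**Conclusion.** The point holds as an internal inconsistency in safety reporting. The instruction in 6.6.2 is narrower than the contraception period in 6.2 and 6.6 and narrower than the reporting duty in 9.7.1. On the assumption that the study ends for a patient at his End of Study visit, about 148 to 162 days of the precaution period fall outside the instruction, or about 169 in the Week 78 nivolumab case. Exposed partner pregnancies in that time may be missed. With 26 patients planned (18 + 8), few events are expected, and no endpoint, analysis set or sample size depends on this. It is a minor point, worth correcting because the correction is nearly free.

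The testing point is secondary: the requirement in 6.6 and the provisions in 8.4, 8.4.8, Table 1 and Appendix 1 do not agree. The documents do not settle which should govern, and this review takes no position on it.

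**What to change.** 1. Reword 6.6.2 so that men are asked to notify the investigator of any partner pregnancy that begins during the study or within the protocol's existing 6-month period after treatment, whenever they learn of it. Use parallel wording in 6.6.1 so that its two conditions are clearly alternatives.
2. State once, for 6.2, 6.6, 6.6.1 and 6.6.2, the event from which the 6 months is counted, including which study drug's last dose is meant.
3. Cross-refer both subsections to 9.7.1, so it is clear that a later pregnancy the site hears of remains reportable. Carry the wording into the patient information.
4. Reconcile the testing requirement for abstinent women in 6.6 with Sections 8.4 and 8.4.8, Table 1, and the Appendix 1 row and footnote 6, so that all say the same thing. The content is for the sponsor and investigators to decide.

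The cost of items 1 to 3 is a few lines of protocol and patient-information text, with no new visit, sample or analysis. Item 4 is also a text change; any further cost depends on how the passages are reconciled.

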#### 6.7 WITHDRAWAL OF CONSENT

Patients who request to discontinue study treatment can remain in the study and continue to be followed for protocol specified follow-up procedures unless the patient wishes to withdraw from study procedures as well as from study treatment. If a patient should wish to withdraw consent for future follow-up (as in Section 6.4) they should notify the Investigator of this decision. The withdrawal of consent should be explained in the medical records by the Investigator, to confirm whether the withdrawal is from further treatment with study drug only, or also from study procedures and/or post treatment study follow-up, and entered on the appropriate eCRF page.

#### 6.8 FURTHER TREATMENT AFTER THE END OF THE STUDY

For patients who leave the study, either due to early withdrawal or completion, normal standard of care (SOC), according to local practice, will continue as necessary.

# 7. STUDY TREATMENT

#### 7.1 INVESTIGATIONAL PRODUCT

#### 7.1.1 Manufacture and Formulation

IMM-101 is formulated at a concentration of 10 mg/mL in borate buffered saline, pH 7.7–8.3. It is supplied in a variety of single use vials containing up to 2.0 mL. The dose volume is 0.1 mL given intradermally over the deltoid muscle. The product is particulate and must be shaken gently before use to re-suspend the particulate matter. It should be stored upright at 2°C to 8°C and protected from light.

Primary manufacture is undertaken to GMP standards at BioElpida, Saint Priest, France. Formulation of drug product and aseptic filling is carried out by Nova Laboratories, Leicester, UK. Rigorous in-process control testing and final product testing against pre-defined specifications provide assurance of the quality of IMM-101.

The batch(es) to be used in this study are comparable to those previously tested in pre-clinical safety studies and the previous Phase 1 and 2 studies.

Batch number(s) and expiry date(s) will be documented, including in the Sponsor File and in the final clinical study report.

Page 42 of 98

# 7.1.2 Packaging and Labelling

IMM-101 will be labelled in local language. The label will contain the information as required by Annex 13 of the GMP guidelines of the European Commission, ICH-GCP guidelines, and other prevailing legislation.

## **7.1.3 Storage**

IMM-101 supplied by the Sponsor is to be used exclusively in the clinical study according to the instructions of this protocol.

The product must be stored in a refrigerator at 2°C to 8°C and protected from light. After the product has been removed from the refrigerator it must be allowed to equilibrate at ambient temperature for 5 to 10 minutes before being used. The product must be used within 6 hours of being removed from the refrigerator or it should be discarded.

IMM-101 must be stored in securely locked areas not generally accessible until administered to the patients. The key to the storage area is to be kept by the Investigator (or delegated person responsible for the study drug). The store will be accessible only to those persons authorised by the Investigator to dispense/administer IMM-101.

Further details on drug handling will be provided in a separate operations manual.

# 7.1.4 Destruction of Surplus Medication

All surplus IMM-101 will be sent for destruction following authorisation from the Sponsor and the destruction documented.

# 7.1.5 Investigational Product Accountability

The Investigator, or an approved representative, must maintain records of the product's delivery to the study site, the inventory at the site, the use for each patient, and will ensure that all investigational products are stored in a secure, limited access area. These records must include dates, quantities, batch/serial numbers, expiry dates, and the unique code numbers assigned to the investigational product(s) and study patients. A temperature log of the medication storage refrigerator must also be kept. Investigators must maintain records that document adequately that the patients were provided with the doses specified by the Protocol and reconcile all investigational product received from the Sponsor.

To ensure adequate records, IMM-101 will be accounted for on an on-going basis throughout the study in drug accountability forms at the study site. Records will be kept in accordance with the applicable regulatory requirements and the Investigator will ensure that IMM-101 is dispensed only by qualified site staff. These records will be independently monitored by a study monitor.

#### **7.1.6 Dosing**

IMM-101 is administered as a single 0.1 mL intradermal injection of IMM-101 (10 mg/mL) into the skin overlying the deltoid muscle, with the arm being alternated between each dose. The Investigator will have been appropriately trained *a priori* in the technique of intradermal injection.

Previous clinical experience with IMM-101 has suggested that this dose is well tolerated. The skin reaction that develops at the site of injection is characterised by erythema, local swelling and occasionally mild ulceration. All symptoms are to be expected given the known pharmacology of the product and previous clinical experience. Furthermore, data from safety

Page 43 of 98

and tolerability studies with IMM-101 have revealed that skin reactions resolve satisfactorily over time and do not impair daily activity.

The first dose of IMM-101 administered to each patient in the study is followed by vital signs monitoring for at least 2 hours under medical supervision with resuscitation facilities available as a precautionary measure.

The treatment regimen will be 1 dose of IMM-101 given every 2 weeks for the first 3 doses followed by a rest period of 4 weeks, then one dose every 2 weeks for the next 3 doses. This is followed by a dose every 4 weeks thereafter with a window of  $\pm$ 2 days allowed.

Nivolumab and ipilimumab are administered according to the prescribing information. When either nivolumab or ipilimumab are administered on the same day as IMM-101, according to the Schedule of Assessments, patients will receive IMM-101 first. The first dose of nivolumab administered to each patient on study is given at least 2 hours after the first dose of IMM-101.

The Study Schedule of Assessments is presented in Appendix 1.

## 7.2 DOSE ADJUSTMENT CRITERIA

# 7.2.1 Dosing delays

The prescribing information for nivolumab and for ipilimumab should be referred to for reasons for withholding or permanently discontinuing these medications. When a dose delay or treatment discontinuation is indicated for nivolumab or ipilimumab based on adverse events, IMM-101 should also be withheld/discontinued in the same manner and the reason for the dose delay recorded in the eCRF. Dosing delays should be applied for any other adverse events considered related to any study drug with the related study treatment(s) withheld until treatment can resume. Dosing delay can also apply to any adverse event, laboratory abnormality, or intercurrent illness which, in the judgment of the Investigator, warrants delaying the dose of study medication(s).

In the event of any immune-mediated adverse reactions of  $\geq$  Grade 3 (severe), IMM-101 and nivolumab (or ipilimumab when used for cohort B) should be withdrawn, either until resolution of the event or permanently, at the discretion of the Investigator. Treatment delays due to Grade 2 immune-related adverse reactions will be assessed on a case-by-case basis by the Investigator.

Permanent discontinuation should be considered for any severe or life-threatening adverse reactions, with the final decision on whether to stop treatment made after discussion with the Sponsor.

Ideally, the nivolumab dosing regimen chosen at the start of the study should be maintained (notwithstanding modifications due to AEs as described above). However, if a 480mg 4-weekly nivolumab dosing is not tolerated, the patient may be switched to a 240mg 2 weekly regimen. The dose of ipilimumab should not be modified for any reason.

The dose of IMM-101 may be reduced in cases of injection site reactions (see Section 7.2.3).

# 7.2.2 Resumption of Dosing

Patients may resume treatment with study drugs when the drug-related AE(s) resolve to Grade  $\leq 1$  or baseline value. In cases where the toxicity does not resolve or improve to  $\leq$ Grade 1 within 12 weeks after last administration of study drug, discontinuation from study therapy should be considered after discussion with the Sponsor.

Page 44 of 98

Patients still at Grade 2 may continue in the study only if asymptomatic and controlled, at the Investigator's discretion. However, drug-related pulmonary toxicity, diarrhoea, or colitis, must have resolved to baseline before treatment is resumed.

When treatment is restarted, the patient should restart treatment at the next scheduled time point per protocol. However, if the treatment is delayed past this point, the next scheduled time point will be delayed until dosing resumes.

Two dosing delays due to the same toxicity will be permitted. In the event of a third occurrence of the same toxicity which would require dosing delay, all study therapy will be discontinued permanently.

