## 3.5 POTENTIAL RISKS AND BENEFITS

Clinical studies with IMM-101 to date have shown promising efficacy signals in metastatic pancreatic cancer and encouraging indications of long-term survival in both this indication and in patients with advanced melanoma. To date, the only adverse drug reactions associated with IMM-101 treatment that have occurred in more than 10% of patients in clinical studies are injection site reactions (14.8%) and pyrexia (10.2%) both of which can be viewed as predicted reactions to exposure to a preparation of mycobacterial antigens. The injection site reactions are consistent for this class of product and have been well tolerated by patients to date in the context of both the Phase 1 and Phase 2 studies, including over extended administration periods of over 2 years in 13 patients.

Clinical experience over this time suggests that repeated administration is well tolerated initially on a monthly administration regimen, however, the incidence and severity of injection site reactions increases over time, and a reduction in dose and/or an increase in the dosing interval may be required after prolonged administration. In IMM-101-002A, 8 of the 12 patients received only full doses (i.e. did not have any dose reduction) over the combined IMM-

Page 28 of 98

101-002/002A study period with the maximum number of full doses received being 31 and few dosing delays. In study IMM-101-008, many patients received half doses after 1 year on study but this was following IMM-101 treatment in IMM-101-001 and on a named patient basis.

Therefore, the Investigator will closely supervise the patients and in the event of unexpectedly severe or long-lasting site reactions will inform the Sponsor and reduce the dose, or delay administration or withdraw the patient from the study after consultation with the Sponsor.

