# 7.2.3 IMM-101 Injection Site Reactions

Injection site reactions are expected and therefore it is important not to withhold IMM-101 in these situations, but to continue at a lower dose and/or with dose interval adjustments. IMM-101 should only be withheld if felt to be necessary by the Investigator and/or patient due to intolerable injection site reactions.

During the study, at the discretion of the Investigator, the dose interval may be modified provided the minimum period between doses is at least 12 days (14±2 days) between visits 1-2, 2-3, 5-6 and 6-7. The 28 day interval ±2 days between other doses (3-5, 7-9 and all after this point) should be maintained, subject to skin reactions or other reasons as detailed above (7.2.1). Administration of nivolumab and, if used in cohort B, for ipilimumab, should continue according to the normal schedule irrespective of any dosing delays for IMM-101 due to injection site reactions.

In the event of an injection site reaction of ≥Grade 3 (severe) as measured by the NCI CTCAE v4.0, at the discretion of the Investigator, patients may be administered a half dose of IMM-101 (i.e., a single 0.05 mL intradermal injection of IMM-101) or the dosing interval may be increased or both. If the dosing interval is increased, the patient should attend the study site for safety assessments at least every 4 weeks.

Any change in the dose of IMM-101 or the frequency at which it is administered must be recorded in the patient's eCRF.

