# 7.3 PERMANENT DISCONTINUATION OF STUDY TREATMENT FOR PATIENTS

The prescribing information for nivolumab and for ipilimumab should be referred to for reasons for permanently discontinuing these medications. When treatment discontinuation is indicated for nivolumab or ipilimumab based on adverse events, IMM-101 should also be discontinued. In the event of any immune-mediated adverse reactions of ≥Grade 3 (severe), IMM-101 and nivolumab (or ipilimumab when used for cohort B) should be withdrawn, either until resolution of the event or permanently, at the discretion of the investigator.

Permanent discontinuation for a patient should be considered for any severe or life-threatening adverse reactions, with the final decision on whether to stop treatment made after discussion with the Sponsor.

A dosing delay due to an adverse event failing to resolve or improve to ≤Grade 1 within 12 weeks after last administration of study drug, may result in discontinuation of a patient from study therapy, at the Investigator's discretion and after discussion with the Sponsor. Two dosing delays due to the same toxicity are permitted on study but a third occurrence of the same toxicity which would require dosing delay, will result in permanent discontinuation of the patient from the study. Patients discontinuing the study will be followed up as in Section 6.4.

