# 9.2.4 Intensity of Adverse Events

All AEs (or toxicities) including local injection site reactions encountered during the study will be evaluated according to the NCI CTCAE v4.03

[23] grading system (0 to 5), where applicable.

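### Protocol 7.2.2 and 7.2.3 conflict on nivolumab or ipilimumab when injection site reactions repeatedly delay IMM-101, and 7.2.2 and 7.3 disagree on whether therapy or study participation ends

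*Protocol*

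**What the plan says.** Protocol 7.2.2 (Resumption of Dosing) gives a general rule: "Two dosing delays due to the same toxicity will be permitted". It continues: "In the event of a third occurrence of the same toxicity which would require dosing delay, all study therapy will be discontinued permanently". Injection site reactions are not excluded.

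Protocol 7.3 (Permanent Discontinuation of Study Treatment for Patients) uses the same trigger with a different outcome: "a third occurrence of the same toxicity which would require dosing delay, will result in permanent discontinuation of the patient from the study". Its next sentence sends such patients to the follow-up in Section 6.4.

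Protocol 7.2.3 (IMM-101 Injection Site Reactions) discourages withholding and prefers a lower dose or an adjusted interval. It still leaves room to withhold: "IMM-101 should only be withheld if felt to be necessary by the Investigator and/or patient due to intolerable injection site reactions". It adds that nivolumab and, where used, ipilimumab "should continue according to the normal schedule irrespective of any dosing delays for IMM-101 due to injection site reactions".

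Protocol 9.2.4 grades "All AEs (or toxicities) including local injection site reactions encountered during the study", so the protocol's own vocabulary treats these reactions as toxicities.

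Protocol 5.1 and 6.4 say that patients who stop treatment for a reason other than progression, and for whom no other treatment is thought suitable or wanted, stay in the study and keep being scanned until progression.

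**The concern.** A site could face a patient whose third intolerable injection site reaction calls for another IMM-101 delay. Section 7.2.2 stops the checkpoint inhibitor, 7.2.3 continues it, and 7.3 takes the patient off the study. No sentence says which section prevails.

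The situation can be foreseen. Protocol 3.5 reports that "the incidence and severity of injection site reactions increases over time", and that a lower dose or longer interval may be needed after prolonged dosing.

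The split between 7.2.2 and 7.3 is wider, because it applies to any toxicity. What is at stake is consistent handling of the same patient across sites, the count of discontinuations in the primary safety endpoint, and whether scans that feed BOR and PFS continue.

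**Working it through.** The plan states no figure to reproduce. The check is a comparison of texts, followed by a short calculation of scale.

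**Step 1. Does the general rule reach injection site reactions?** As written, it can. Section 9.2.4 groups them with toxicities, 7.2.3 itself speaks of IMM-101 dosing delays caused by them, and 7.2.2 has no carve-out.

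**Step 2. Apply each section to one patient:** no progression, and a third intolerable site reaction that would require an IMM-101 delay.

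| Protocol section | IMM-101 | Nivolumab or ipilimumab | Study participation |
|---|---|---|---|
| 7.2.2 | stopped for good | stopped for good | not addressed |
| 7.2.3 | may be withheld; no limit on the number of delays | continues on schedule | not ended |
| 7.3 | ends with the study | ends as study treatment | ended, with referral to 6.4 |
| 5.1, 6.4 | – | – | continues with scans, if no further treatment is suitable or wanted |

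Rows 1 and 2 disagree on the checkpoint inhibitor. Rows 1 and 3 disagree on what ends. Row 3 refers to a section (row 4) that assumes some of these patients are still in the study.

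**Step 3. For other toxicities,** 7.2.3 does not apply and the first disagreement disappears. The second remains.

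**Step 4. Is a third delay possible?** Appendix 1 schedules IMM-101 at Weeks 0, 2, 4, 8, 10 and 12 (6 doses), then every 4 weeks from Week 16 to Week 76: (76 − 16)/4 + 1 = 16 doses. The total is 6 + 16 = 22. A reaction to IMM-101 cannot delay the first dose, so 22 − 1 = 21 doses could be delayed. A third delay is feasible, but the documents give no rate.

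**Step 5. Where it reaches the analysis.**
- *Safety.* SAP 5.15.1 counts treatment-emergent events leading to IMM-101 discontinuation and those leading to study withdrawal in separate rows. The patient in Step 2 could appear in neither row (7.2.3), in the first (7.2.2), or under study withdrawal (7.3). This requires the reaction to be recorded as an adverse event. Under Protocol 9.5 that is at the investigator's judgement, but expected from Grade 3 upwards.
- *PFS.* Protocol 10.2 and SAP 5.13.2.1 censor patients without progression or death at the last evaluable scan. If leaving the study ends scanning, censoring comes early.
- *BOR and ORR.* SAP 5.13.1 runs BOR to the last scan on study, and in cohort B no later than the last scan before any ipilimumab. Protocol 5.2.1 closes the window at the end of study treatment. Either window can be shortened.
- *Size.* With the planned 18 and 8 patients, one changed response category moves ORR by 1/18 = 5.6 percentage points in cohort A or 1/8 = 12.5 points in cohort B. A patient whose response is already confirmed moves it by nothing.

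**The case against.** The strongest reply is that 7.2.3 is the specific rule for injection site reactions and naturally overrides the general one. Section 7.2.1 already points to it for dose reduction. Under 7.2.3 a site reaction does not normally require a delay, since dosing is meant to continue with adjustments at the investigator's discretion. This narrows the clash, and that part stands. A reader might infer that any third interval change for a site reaction forces all therapy to stop. The text does not support that, because the trigger is a toxicity that would require a delay. The precedence of 7.2.3 is plausible, but it is stated nowhere.

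Second, 7.3 is headed as a rule about treatment and refers to 6.4, so its mention of the study may be loose wording. That is fair, and it means 7.3 cannot be read as ending scans for everyone. But 6.4 protects only patients for whom no further treatment is suitable or wanted. A patient who goes on to other treatment, including standard care under Protocol 6.8, is not covered. Precedence of 7.2.3 would not repair this mismatch either.

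Third, prior experience suggests few cases. Protocol 3.5 reports that 8 of 12 patients in IMM-101-002A had only full doses, with few delays. Protocol 18.3 reports no site reaction that required treatment to stop. So the documents show that third delays are possible, not that they are likely.

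Finally, all endpoints are descriptive, and neither document censors PFS merely because study treatment stops. A reader might infer that BOR and PFS will be truncated. That follows only if scanning stops.

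**Conclusion.** The point holds in a limited form. There are two inconsistencies:

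1. Sections 7.2.2 and 7.2.3 conflict on the checkpoint inhibitor. This is confined to injection site reactions that repeatedly lead to an IMM-101 delay, chiefly those intolerable enough for it to be withheld.
2. Sections 7.2.2 and 7.3 conflict, for any toxicity, on whether therapy or study participation ends. The wording of 7.3 does not fit 5.1 and 6.4.

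The likely effect is small. It rests on an unknown number of third occurrences, which may be zero. The ORR figures of 5.6 and 12.5 points are upper limits for one patient at the planned cohort sizes. They assume that the rule followed changes that patient's response category. The safety rows can change without that assumption, provided the event is recorded as an adverse event. In cohorts this small, contradictory rules on treatment and scan follow-up should still be corrected. Nothing here indicates which clinical rule is right.

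**What to change.** Amend Protocol 7.2.2, 7.2.3 and 7.3 so that together they state:

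- whether the third-occurrence rule covers injection site reactions;
- which of IMM-101, nivolumab and ipilimumab it applies to;
- whether it ends study therapy or study participation.

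Scan follow-up after such a stop should agree with 5.1 and 6.4, and the text should say what happens to patients who go on to other treatment. The clinical content is for the sponsor and investigators to decide. The cost is a clarifying protocol amendment, with no change to sample size or statistical method. If patients have already met the rule, the data review meeting described in SAP 5.6 should record which section each site followed.
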